Period 1: Day 1 - Day 10 (to 14)

- Participants will receive one of the following antiplatelet medication regimens for 10 to 14 days:
 - No IMP
 - No aspirin but a loading dose of ticagrelor (180 mg) taken on the last day of the medication period, 1 hour prior to endotoxin injection
 - Aspirin (aspirin lysine) 20 mg BD (only)
 - Aspirin (aspirin lysine) 20 mg BD, and a loading dose of ticagrelor (180 mg) taken on the last day of the medication period, 1 hour prior to endotoxin injection
 - Aspirin (aspirin lysine) 75 mg OD (only)

- Aspirin (aspirin lysine) 75 mg OD, and a loading dose of ticagrelor (180 mg) taken on the last day of the medication period, 1 hour prior to endotoxin injection
- Aspirin (aspirin lysine) 300 mg OD (only)
- Aspirin (aspirin lysine) 300 mg OD, and a loading dose of ticagrelor (180 mg) taken on the last day of the medication period, 1 hour prior to endotoxin injection

Visit 3 - Period 1: Day 11 (to 15)

On arrival

- Vital signs
- Physical examination
- Adverse event recording
- Concomitant medication recorded
- IMP compliance check for period 1
- Medically-qualified member of the research team to confirm that the withdrawal criteria (section 7.10) are not met, prior to proceeding further with visit

-1 hour (1 hour before endotoxin injection)

- IV cannula insertion (x2, one in each arm)
- 35.5 ml venous blood sample for baseline lab safety (full blood count, urea & electrolytes [sodium, potassium, urea and creatinine], liver function tests, clotting screen), cytokines, prostanoids, inflammatory markers and platelet function
- Bleeding time measurement
- Urine sample for prostanoid assessment at baseline
- Receive last dose of aspirin of period 1, or last dose of aspirin plus a loading dose of ticagrelor (180 mg), or no IMP, as directed by randomisation allocation
- Collect unused study medication and perform drug accountability check (sachet/pill count)
- Infusion of 250 ml 0.9% saline over 30 minutes
- 23 ml venous blood at 60 minutes after last dose of oral antiplatelet medication or equivalent time if not receiving IMP during period 1 (just before endotoxin administration)

0 hour (time of endotoxin injection)

- Continuous cardiac monitoring starts
- *E.coli* endotoxin 2 ng/kg intravenously administered over 1 minute
- Vital signs at 5, 15 and 30 minutes post-endotoxin
- Continuous IV infusion of 250 ml 0.9% saline over 1 hour
- 14 ml venous blood sample at 30 minutes post endotoxin

1 hour post endotoxin injection

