APPENDIX 1 Sample collection plan

Visit	Visit description	Timepoint within visit	Safety (FBC)	Safety (Chemistry)	Safety (Clotting screen)	DNA/RNA for storage	Plasma for cytokines/storage	Serum for prostaglandins/CRP /storage	Plasma for LTA	Blood for white cell count and subsets/storage	Total for timepoint	Urine	Bleeding time
		Tube type ↳	EDTA	SST	Citrate	EDTA	Citrate	SST	Citrate	Citrate			
Whole blood to draw (ml)													
1	Enrolment		4	4	4.5						12.5		
2	Randomisation			4	4	4.5		5	9	4.5	27	✓	✓
3	Endotoxin day 1	Baseline (pre drug dose)	4	4	4.5		4.5	5	9	4.5	35.5	✓	✓
	Post drug dose/pre endotoxin						4.5	5	9	4.5	23		
	30 mins post endotoxin						4.5	5		4.5	14		
	1 hour post endotoxin						4.5	5		4.5	14	✓	
	1.5 hours post endotoxin						4.5	5		4.5	14		
	2 hours post endotoxin						9	5		9	23	✓	
	3 hours post endotoxin						4.5	5	9	4.5	23	✓	
	4 hours post endotoxin						4.5	5		4.5	14	✓	
	6 hours post endotoxin						4.5	5		4.5	14	✓	
4	(Telephone call only)										0		
5	(Telephone call only)												
6	Start of period 2		4	4	4.5						12.5		
7	Endotoxin day 2	Baseline (pre drug dose)	4	4	4.5		4.5	5	9	4.5	35.5	✓	✓
	Post drug dose/pre endotoxin						4.5	5	9	4.5	23		
	30 mins post endotoxin						4.5	5		4.5	14		
	1 hour post endotoxin						4.5	5		4.5	14	✓	
	1.5 hours post endotoxin						4.5	5		4.5	14		
	2 hours post endotoxin						9	5		9	23	✓	
	3 hours post endotoxin						4.5	5	9	4.5	23	✓	
	4 hours post endotoxin						4.5	5		4.5	14	✓	
	6 hours post endotoxin						4.5	5		4.5	14	✓	
8	(Telephone call only)										0		
9	(Telephone call only)										0		
TOTAL			16	16	18	4	99	95	63	94.5	401		

EDTA, Ethylenediaminetetraacetic acid; LTA, light transmittance aggregometry; SST, serum separator tube. See main text of protocol for other abbreviations.

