2. AUC of the graph of plasma TNF- $\alpha$  over time following endotoxin administration (measured at 0, 0.5, 1, 1.5, 2, 3, 4 and 6 hours post-endotoxin) compared between each aspirin regimen (control, 20 mg BD, 75 mg OD, 300 mg OD, each without ticagrelor) and each corresponding DAPT regimen (control, 20 mg BD, 75 mg OD, 300 mg OD, each with ticagrelor 90 mg BD) by paired t-tests.
3. Plasma IL-6 at 2 hours following endotoxin administration, compared between each aspirin regimen (control, 20 mg BD, 75 mg OD, 300 mg OD, each without ticagrelor) and each corresponding DAPT regimen (control, 20 mg BD, 75 mg OD, 300 mg OD, each with ticagrelor 90 mg BD) by paired t-tests.

4. AUC of the graph of plasma IL-6 over time following endotoxin administration (measured at 0, 0.5, 1, 1.5, 2, 3, 4 and 6 hours post-endotoxin) compared between each aspirin regimen (control, 20 mg BD, 75 mg OD, 300 mg OD, each without ticagrelor) and each corresponding DAPT regimen (control, 20 mg BD, 75 mg OD, 300 mg OD, each with ticagrelor 90 mg BD) by paired t-tests.
5. Change in serum CRP over time following endotoxin administration (measured at 0 and 6 hours post-endotoxin) compared between each aspirin regimen (control, 20 mg BD, 75 mg OD, 300 mg OD, each without ticagrelor) and each corresponding DAPT regimen (control, 20 mg BD, 75 mg OD, 300 mg OD, each with ticagrelor 90 mg BD) by paired t-tests.
6. AUC of the graph of serum TXB2 over time following endotoxin administration (measured at 0, 0.5, 1, 1.5, 2, 3, 4 and 6 hours post-endotoxin) compared between each aspirin regimen (control, 20 mg BD, 75 mg OD, 300 mg OD, each without ticagrelor) and each corresponding DAPT regimen (control, 20 mg BD, 75 mg OD, 300 mg OD, each with ticagrelor 90 mg BD) by paired t-tests.
7. AUC of the graph of urinary PGI-M (measured at 0, 2, 4 and 6 hours, each adjusted for [divided by] urinary creatinine) over time following endotoxin administration compared between each aspirin regimen (control, 20 mg BD, 75 mg OD, 300 mg OD, each without ticagrelor) and each corresponding DAPT regimen (control, 20 mg BD, 75 mg OD, 300 mg OD, each with ticagrelor 90 mg BD) by paired t-tests.

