2. Plasma IL-6 over time following endotoxin administration (measured at 0, 0.5, 1, 1.5, 2, 3, 4 and 6 hours post-endotoxin) assessed between treatment groups (control vs. 20 mg BD vs. 75 mg OD vs. 300 mg OD, with or without ticagrelor) using a mixed effect linear model with patient as a random effect, aspirin dose, presence or absence of ticagrelor treatment and treatment period (first or second) as fixed effects, and baseline value as covariate.
3. Change in serum CRP over time following endotoxin administration (measured at 0 and 6 hours post-endotoxin) assessed between treatment groups (control vs. 20 mg BD vs. 75 mg OD vs. 300 mg OD, with or without ticagrelor) using a mixed effect linear model with patient as a random effect, aspirin dose, presence or absence of ticagrelor treatment and treatment period (first or second) as fixed effects, and baseline value as covariate.

4. Serum TXB2 over time following endotoxin administration (measured at 0, 0.5, 1, 1.5, 2, 3, 4 and 6 hours post-endotoxin) assessed between treatment groups (control vs. 20 mg BD vs. 75 mg OD vs. 300 mg OD, with or without ticagrelor) using a mixed effect linear model with patient as a random effect, aspirin dose, presence or absence of ticagrelor treatment and treatment period (first or second) as fixed effects, and baseline value as covariate.
5. Urinary PGI-M (measured at 0, 2, 4 and 6 hours, each adjusted for [divided by] urinary creatinine) over time following endotoxin administration, assessed between treatment groups (control vs. 20 mg BD vs. 75 mg OD vs. 300 mg OD, with or without ticagrelor) using a mixed effect linear model with patient as a random effect, aspirin dose, presence or absence of ticagrelor treatment and treatment period (first or second) as fixed effects, and baseline value as covariate.
6. Serum PGE2 over time following endotoxin administration (measured at 0, 0.5, 1, 1.5, 2, 3, 4 and 6 hours post-endotoxin) assessed between treatment groups (control vs. 20 mg BD vs. 75 mg OD vs. 300 mg OD, with or without ticagrelor) using a mixed effect linear model with patient as a random effect, aspirin dose, presence or absence of ticagrelor treatment and treatment period (first or second) as fixed effects, and baseline value as covariate.

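### The PGI-M value analysed as 0 h is collected before ticagrelor is given, so the ticagrelor contrasts that include it are diluted

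*SAP*

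**What the plan says.** Every PGI-M analysis in the SAP uses the times 0, 2, 4 and 6 h. The early-termination model (10.6, item 5) takes "Urinary PGI-M (measured at 0, 2, 4 and 6 hours, each adjusted for [divided by] urinary creatinine" as its outcome. The monotherapy versus combination comparison (10.3.3, item 7) uses the "AUC of the graph of urinary PGI-M (measured at 0, 2, 4 and 6 hours". Items 6, 16 and 17 of 10.3.3 name the same four times. Protocol 3.3 declares the endpoint as an AUC over 0 to 6 h.

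The collection schedule differs. In Protocol 7.7, the block one hour before endotoxin at visits 3 and 7 lists "Urine sample for prostanoid assessment at baseline", and after it the dosing step: "Receive last dose of aspirin of period 1, or last dose of aspirin plus a loading dose of ticagrelor (180 mg". What follows just before endotoxin is blood only: "23 ml venous blood at 60 minutes after last dose of oral antiplatelet medication". Appendix 1 agrees. Urine is ticked in the row "Baseline (pre drug dose" and not in the row "Post drug dose/pre endotoxin".

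The sampling list at the end of 7.7 gives PGI-M a single pre-endotoxin sample. TNF-α, IL-6 and TXB₂ have two: one before the last dose, and one after it but before endotoxin.

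**The concern.** A sample taken before ticagrelor cannot respond to ticagrelor. If it enters the outcome as the first point of the response, any contrast between visits with and without ticagrelor is averaged with a value whose expected difference is zero. The contrast shrinks towards no effect and the test loses power. The blood markers escape this because they have a post-dose, pre-endotoxin sample to serve as 0 h. PGI-M is a listed secondary endpoint, and whether ticagrelor modifies aspirin's effects is a stated aim of the sample analysis (Protocol 7).

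**Working it through.** **Inputs.** Analysis times are from SAP 10.3.3 and 10.6. Sampling order is from Protocol 7.7 (visits 3 and 7) and Appendix 1. The documents give no size, time course or SD for a ticagrelor effect on PGI-M, and no dilution or power figure for it, so there is no plan figure to reproduce. In Appendix 1 as read from the PDF, column positions are uncertain. The post-dose, pre-endotoxin row carries no tick at all, so the reading does not depend on them.

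**Step 1: which analyses contain a ticagrelor contrast.**

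| Analysis | Groups compared | Ticagrelor contrast? |
|---|---|---|
| 10.3.3 item 6 | aspirin regimens, all without ticagrelor | no |
| 10.3.3 item 17 | aspirin regimens, all with ticagrelor | no |
| 10.3.3 item 7 | with v without, paired t-tests on AUC | yes |
| 10.3.3 item 16 | three-way ANOVA | yes (main effect averages the four times) |
| 10.6 item 5 | mixed model, no time term listed | yes |

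**Step 2: weight of the pre-dose value.** Trapezoid on 0, 2, 4, 6 h: AUC = y0 + 2·y2 + 2·y4 + y6. The weights sum to 6, so y0 has 1/6 = 16.7%. Mean of four values: y0 has 1/4 = 25%.

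**Step 3: dilution relative to the post-dose effect.** Let d2, d4, d6 be the ticagrelor effects at 2, 4, 6 h, with d0 = 0 by design.

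- AUC: (0 + 2·d2 + 2·d4 + d6)/6, against (2·d2 + 2·d4 + d6)/5 from the post-dose values with the same weighting. Ratio 5/6, so 16.7% too small.
- Mean: (0 + d2 + d4 + d6)/4, against (d2 + d4 + d6)/3. Ratio 3/4, so 25% too small.

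Both ratios hold whatever the profile over 2 to 6 h. They apply on the scale on which the values are combined; if an AUC is logged afterwards, they are approximate.

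**Step 4: loss relative to a true post-dose 0 h sample.** This is w0·d0 / Σ(w·d), where d0 is now the effect that such a sample would have shown. It depends on an assumed time course:

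| Assumed effect at 0, 2, 4, 6 h | AUC | Mean |
|---|---|---|
| 0, 1, 1, 1 | 0% | 0% |
| 0.25, 1, 1, 1 | 0.25/5.25 = 4.8% | 0.25/3.25 = 7.7% |
| 0.5, 1, 1, 1 | 0.5/5.5 = 9.1% | 0.5/3.5 = 14.3% |
| 1, 1, 1, 1 | 1/6 = 16.7% | 1/4 = 25% |
| 1, 0.75, 0.5, 0.25 | 1/3.75 = 26.7% | 1/2.5 = 40% |

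**Step 5: what removes it.** Plotting the sample at its actual time (-1, 2, 4, 6 h) gives weights 1.5, 2.5, 2, 1 out of 7, so the pre-dose value would have 1.5/7 = 21.4%. Relabelling alone does not help. Adding the collected but unused 1 h urine while keeping the pre-dose value as 0 h leaves 0.5/6 = 8.3% (AUC) or 1/5 = 20% (mean of five). Limiting the outcome to post-endotoxin samples gives 0%.

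A 150-run simulation of the 10.6 item 5 model (46 participants, 37 with both periods, assumed variances) gave 0.747 of the true ticagrelor effect with the pre-dose value as an outcome row, and 0.996 with post-dose outcomes only. Many fits gave convergence warnings. The conclusion rests on the weights above, which the simulation matches.

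**The case against.** A reader might infer that every PGI-M analysis understates ticagrelor by 17-25%. The documents do not support that, for four reasons:

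- Items 6 and 17 compare aspirin regimens with ticagrelor absent throughout or present throughout, so there is no ticagrelor effect to dilute.
- The range measures loss against the 2-6 h effect. The declared endpoint is AUC from 0 to 6 h, and against a true 0 h sample the loss could be nil or larger than 25% (step 4).
- Item 16 has timepoint as a factor. A ticagrelor-by-time term could still show the effect, with the pre-dose point as a natural reference; only the main effect is averaged.
- In 10.6 item 5 the loss is nil if the pre-dose value serves only as the baseline covariate.

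All four stand as limits. On the last, the more natural reading keeps 0 h as an outcome. Item 5 lists it among the measurement times and names the baseline value separately, and the 7.7 sampling list defines baseline as visit 2. But the visit 3 and 7 schedules also call the -1 h urine baseline, so the text does not settle it.

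A second tempting inference is bias between aspirin regimens, because the pre-dose value falls about 12 h after the previous dose on the twice-daily regimen and about 24 h after it on the once-daily ones (Protocol 8.6). After 10 to 14 days of dosing, though, this is a legitimate on-treatment value, and the dosing interval is part of the regimen being compared. No bias is shown.

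It is also fair that only TNF-α at 2 h is powered, that no hypothesis about ticagrelor and PGI-M is stated, and that both periods use the same pre-dose time. A false positive does not arise. This limits the importance of the point but does not remove it.

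**Conclusion.** The point holds in a limited form. On the visit schedules and Appendix 1 there is no post-dose urine at 0 h, and the value analysed as 0 h precedes ticagrelor. Relative to the effect in the 2, 4 and 6 h samples with the same weighting, the ticagrelor contrast is 1/6 (about 17%) too small in the four item 7 paired tests and 1/4 too small in the item 16 main effect. It is also 1/4 too small in 10.6 item 5, provided that 0 h is an outcome row there. These fractions need no assumption about the effect's shape over 2 to 6 h. Loss relative to a true 0 h sample cannot be fixed from the documents. Some power is lost, but how much cannot be stated without an SD for PGI-M, which the documents do not give. The aspirin-regimen comparisons in items 6 and 17 need only a corrected time label.

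**What to change.** - In the Protocol 7.7 sampling list and throughout the SAP, relabel the first endotoxin-day urine as -1 h, pre-dose. For items 6 and 17 this is the only change.
- In 10.3.3 items 7 and 16 and in 10.6 item 5, restrict the PGI-M outcome to post-endotoxin urine, and state whether the collected 1 h sample is included.
- In those three analyses, use the same-visit pre-dose value as covariate. For item 7, this means regressing the within-participant difference in post-endotoxin AUC on the difference in pre-dose values; the intercept is the ticagrelor effect.
- In 10.6 item 5, define the baseline value as that pre-dose sample.
- Amend the AUC 0-6 h endpoint in Protocol 3.3 to match.

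Cost: an amendment to protocol and SAP text, and no new samples. The declared AUC window becomes shorter, and item 7 changes from a plain paired t-test to an adjusted one. The pre-dose value is already on aspirin, so in item 16 and 10.6 item 5 the aspirin term is conditional on it. The SAP should say that the adjusted fit is read for the ticagrelor term, and that the aspirin term comes from the same model with the visit 2 value as covariate.

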## **10.7 Participant population**

- The pharmacodynamic analysis set will include all participants who achieve at least 80% compliance with study medication during each of the two periods and who complete both endotoxin injection days.
- The safety analysis set (for the purposes of adverse event reporting etc.) will include any participant randomised into the trial that received at least one dose of trial drug or one dose of intravenous endotoxin.

## **10.8 Procedure(s) to account for missing or spurious data**

- Missing data will be recorded by notating 'NR' (not recorded) in the relevant section of the CRF

- Where analysis is performed using ANOVA, missing data will be estimated by multiple imputation using the IBM SPSS software package. Sensitivity analyses will be carried out to report the robustness of this approach.

#### **10.9 Other statistical considerations.**

Not applicable to this study

#### **10.10 Economic evaluation**

Not applicable to this study.
